Aim 2: To determine the impact of sublingual administration of a CBD extract on psychological factors known to influence pain intensity and duration. The investigation of psychological constructs will include evaluating the effects of sublingual administration of a CBD extract on pain-related anxiety, catastrophizing and fear pertaining to participants' views and perceptions toward engaging in strenuous physical exercise, sustaining a musculoskeletal injury and prolonged symptomatic and functional recovery. We hypothesize that the anxiolytic effects of sublingual administration of a CBD extract will diminish the threat and perceived physical stress of exercise-induced pain, physical harm, and prolonged symptomatic and functional recovery.

This exploratory study will provide preliminary data needed to support the hypotheses of a planned larger scale application. Preliminary data will help in better designing a future study aimed at identifying an efficacious dose range of hemp-derived CBD extract, as well as determining the cellular and molecular mechanisms that contribute to symptom resolution and recovery. Our findings may also be helpful for making future improvements for treating a broader range of inflammatory conditions that afflict the musculoskeletal system.

6. Research Plan:

Study Location & Design

The project will involve one study center located on the campus of the University of Florida. Data collection for the study will take place in the Sports Medicine & Human Performance Research Laboratory ([name]). The study protocol will be submitted to the UF Gainesville Health Science Center Institutional Review Board (IRB-01) located in the Gainesville Health Science Center ([name]).

The design will be a double-blind, randomized, vehicle-controlled, three-arm trial. Participants will be randomly assigned to either an active CBD dose group (n=15) or vehicle-control (placebo) group (n=15).. The effects of the active CBD dose groups will be compared to the vehicle-control. Subjects will be required to complete a 15-day study trial spanning a presupplement baseline visit, a controlled daily dosage regimen, pre-exercise baseline testing, eccentric exercise to induce muscle damage, and planned follow-up post-exercise data collection time points.

Study Population

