Inclusion Criteria: a) male and female adults between the ages of 18-35 years and b) English speaking, and c) both female and male subjects must be currently practicing acceptable methods of birth control, such as abstinence, and methods of contraception (barriers, oral, patch or other prophylactic methods).

Exclusion Criteria: (a) use of cannabis products on a regular basis OR positive urine test for cannabis, (b) history of seizure disorder (self or family), traumatic brain injury, liver, kidney, or cardiovascular disease, (c) current medical condition that would prevent the participant from performing strenuous resistance exercise, (d) weight lifting for the lower extremities (legs) more than twice a week, (e) currently experiencing pain in the hips, leg, or knee region, (f) pregnancy, lactating or positive urine pregnancy test, (g) known allergy to CBD, coconut/sesame oil, or tree nuts (coconut).

If the participant self-reports that they are currently using tobacco products or a nutritional/dietary supplement, or if they take prescription anti-depressant/anxiety medications, the participant may continue to use the product(s) but they must be on a stable dose at least 3 months prior to randomization as well as during the 15-day study trial period. Also, if the participant is currently using OTC anti-inflammatory medication (e.g., Advil, Aleve, Aspirin) on a regular basis, we will ask that they stop taking the medication at least 7 days before randomization and refrain from using the product during their participation in the study trial.

Investigational Product & Dosing Schedule

Participants will be provided a 30mL bottle with a syringe dropper on day 1 with instructions to ingest the solution orally using a sublingual route of administration (0.5 cc ~1/2 dropper) twice per day (BID) 12 hours apart (morning and evening) at the prescribed daily dosages: Vehicle-control (0mg/30mL hemp extract = no hemp extract), and active Dose (2000mg/30mL hemp extract = 67mg/day). The sublingual route of administration allows the product to be absorbed directly into venous circulation, and thus bypasses the liver and eliminates the consequences of first pass metabolism; ultimately increasing its bio-availability. The bioavailability of CBD administered orally (including sublingual) is estimated to be 13-19% and its half-life estimated to be around 18-32 hours. 35,36

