- 2. Participant is unwilling to continue in the study.
- 3. Lack of compliance with protocol.
- 4. Investigator or study sponsor stops the study for any reason.
- 5. Participant becomes pregnant.
- 6. Participant is enrolled in error or lost to follow-up (lost to follow-up will be defined as a subject failing to attend planned study visits or failure to respond to contacts by study personnel after documented 2 attempts).

*Potential Side Effects and/or Adverse Events (AEs):

- Feelings of anxiety (nervousness, restlessness or being tense, feelings of danger, panic, or dread), paranoia, or negative mood (depression or suicidal thoughts), or paranoia.
- 2. Poor quality of sleep (persistent insomnia).
- 3. Feelings of extreme fatigue, sleepiness or drowsiness.
- 4. Feelings of nausea (upset stomach, vomiting or gastro-intestinal (GI) distress (e.g. diarrhea).
- 5. Change in or loss of appetite.
- 6. Feelings of light-headedness or dizziness.
- 7. Visual disturbances such as blurry/double vision or dilated pupils.
- 8. Hypotension, hypertension, tachycardia, heart palpitations, syncope or dyspnea.
- 9. Development of a skin rash with redness and itching.
- 10. Loss of muscle coordination (clumsiness)
- 11. Muscle spasms

Visit 1 (Consenting, screening, randomization and test product distribution, Day 1)

Participants will be consented. Consenting will be performed by one of the co-investigators in a private room. The following procedures will be performed: urine sample for pregnancy (females) and toxicology screen (presence of cannabinoids), a brief physical exam (including vital signs: measurements for height, weight, pulse, blood pressure and body temperature), obtaining a thorough medical and psychiatric history, including a review of past medical history, concomitant medications, inclusion/exclusion criteria and potential contraindications, assessment of the oral cavity and sublingual area to rule out any active lesions or abnormalities (bleeding, sores, ulcers, abscesses, etc.). If any lesions are found to be present, the research assistant will document the findings and follow up with a consultation phone call with the study physician to determine next steps. The study participant may choose to be excluded from participation or wait until the condition fully resolves. If the participant continues with the study protocol, follow up oral assessments will be repeated at visits 2 through 6.

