Results of urine screening for pregnancy and toxicology (presence of cannabinoids) will be available and assessed during the first visit. If the urine test (pregnancy or cannabinoids) comes back positive, the participant will be excluded from the study. The participant will complete several psychological questionnaires (FPQ-9, PCS, PASS-20, PSQI, & LEFS), followed by tests for muscle soreness and quantitative sensory testing (QST). Each participant will be provided a detailed safety monitoring checklist of side effects and/or adverse reactions that they may potentially experience from ingesting the investigational product. Participants will then be instructed on how to perform their own passive surveillance for identifying these side effects/adverse events and what to do if they experience any of them between study visits while they are ingesting the investigational test article (Days 1 through 10). Participants will be instructed to maintain current activity levels and not to initiate a resistance-training or weightloss program for the duration of the study. Participants will then be randomly assigned to an experimental group and instructed on how to ingest the investigational test article (or placebo) and dosing procedures, which will be dispensed in a quantity to last for the next 15 days. Each participant will be provided a daily log chart to record their daily CBD doses for compliance and monitoring purposes. A pre-exercise visit will be scheduled. Each subject will receive \$10 for completion of the test session.

During the passive surveillance period (Days 1 through 10) participants will be instructed to contact the PI ([name]) if they experience any of the side effects/adverse events from the checklist provided at the baseline visit. [name]/[name] will then contact the study physician ([name]) for consultation. The side effects/adverse reactions will be triaged as mild, moderate or severe, and a determination will be made as to whether the side effect/adverse reaction is due to the investigational product or some other circumstance (e.g. food poisoning). If the event is determined to be due to the investigational test article and graded moderate to severe by the study physician, the participant will then be instructed to stop participation and seek medical care by their primary physician or hospital. Any participant that reports a serious adverse event will be followed to full resolution.

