Visit 2 (Pre-exercise measurements and exercise protocol, Day 11)

Participants will be assessed actively (including vital signs) at each subsequent visit by study personnel using the side effects/adverse events checklist. Each participant will be read each side effect/adverse reaction from the checklist and instructed to self-report as yes (go) or no (no go). For participants who continue in the study, the following procedures will be performed: completion of psychological questionnaires (FPQ-9, PCS, PASS-20, PSQI, & LEFS), followed by tests of muscle soreness, quantitative sensory testing (QST), the timed stair climbing test (TSCT) and isometric strength measures to evaluate leg function. Participants will then undergo a standardized single bout of eccentric resistance exercise to the dominant quadriceps muscle. An isokinetic dynamometer (Biodex System 4 Pro, Biodex Medical Systems, Inc., Shirley, NY) will be used for the eccentric exercise protocol. Each participant will then perform five sets of twenty-five repetitions. Exercise will be performed using concentric (meaning shortening of muscles during contraction) and eccentric (lengthening of the muscle while still developing tension). The angular velocity will be set at 60°/sec for concentric and 90°/sec for eccentric actions. Participants will be given a three-minute rest period between sets. Each subject will receive \$15 for completing the test session.

Visit 3, 4, & 5 (Follow-up measurements @ 24, 48, & 72-hr post-exercise, Day 12, 13, & 14)
The following procedures will be performed: completion of psychological questionnaires (PCS & LEFS), followed by tests of muscle soreness and leg function testing (TSCT and isometric strength measures). Participants will receive \$5 for completing visits 3, 4 and 5.

Visit 6 (Follow-up measurements @ 96-hr post-exercise, Day 15)

The following procedures will be performed: completion of psychological questionnaires (FPQ-9, PCS, PASS-20, PSQI, & LEFS), followed by tests of muscle soreness, QST, and leg function testing (TSCT and isometric strength measures). At the end of the session each participant will be asked if they thought they were taking the active CBD product or placebo. Participants will receive \$10 for completing visit 6.

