Participants will be informed during the consenting period, both in writing on the consent form and verbally, that participants will likely experience soreness and stiffness within the exercised muscles after completing the exercise protocol. We postulate that participants will likely experience some level of heightened fear and anxiety (pain-related or other) in the 10-day wash-in phase of the investigational test article before they undergo the experimental exercise protocol and recovery phase. We feel this will be quantifiable on the self-reported psychological questionnaires that the participants will complete before and after the experimental protocol.

Data Management & Analysis

All information and data collected will be stored in locked filing cabinets or in computers with security passwords and accessed only by members of the research team. This process facilitates

data entry and collection, allows for participants to complete self-report questionnaires, and offers optimal security for collecting research-related information. The proposed Data Management will be housed within the Human Performance Laboratory and a secure webbased platform approved by UF (e.g. Redcap) will be used.

Outcome measures will be analyzed using a two-way ANOVA with repeated measures (between-group; within-time) or distribution free test (e.g Friedmans) as indicated by data distribution. Statistical significance will be set at p<0.05. If significant interactions occur, the Tukey post-hoc test will be used to reveal where the differences occur. We will calculate effect sizes and estimates of precision for all outcomes. All data analyses will be performed using SPSS® for Windows 16.0 (SPSS, Inc., Chicago, IL).

A **Data and Safety Monitoring Plan** will consist of two components: (1) overseeing participant safety and data monitoring, and (2) performance of monitoring. Since this project is viewed as low potential risk, all key personnel will perform all data and safety monitoring on an as needed basis.

7. Possible Benefits:

There is no known direct benefit from participating in this study. Study participants have the option of being paid for their time performing research related duties or they may choose to receive extra credit for a course they are currently taking and that may or may not be considered a benefit. There are no other obvious benefits to the study participant.

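### Cheap improvement: name a rank test that compares the arms in place of Friedman's, analyse the peak and duration outcomes as two-group comparisons, and use all available visits instead of complete rows only

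*Combined protocol and SAP*

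**What the plan says.** Section 6, Data Management & Analysis, gives one plan for every outcome: "Outcome measures will be analyzed using a two-way ANOVA with repeated measures (between-group; within-time", or a "distribution free test (e.g Friedmans) as indicated by data distribution". Tukey comparisons follow a significant interaction, at the 0.05 level. It also promises: "We will calculate effect sizes and estimates of precision for all outcomes". It names no sphericity correction, rule for missed visits, analysis population or covariate.

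The comparison of interest is under Study Location & Design, with 15 per arm: "The effects of the active CBD dose groups will be compared to the vehicle-control".

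The visit descriptions give three schedules:
- Soreness, LEFS and PCS: all six visits.
- MVIC and TSCT: Visits 2 to 6.
- QST, FPQ-9, PASS-20 and PSQI: Visits 1, 2 and 6.

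Visit 1 measures come before allocation ("Participants will then be randomly assigned to an experimental group and instructed on how to ingest the investigational test article"). Visit 2 is taken on product but before the injury ("Visit 2 (Pre-exercise measurements and exercise protocol, Day 11").

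Primary Outcome Measures defines peak soreness, duration of soreness and peak disability. Each is one number per person.

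**The concern.** Four features of the plan do not fit its purpose.

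1. **Fallback test.** Soreness is a bounded 0 to 10 scale and LEFS a bounded score, and entry excludes people "currently experiencing pain in the hips, leg, or knee region". Skewed data are therefore plausible. If they led to Friedman's test, the result would say that soreness changes over the visits, which the injury model guarantees. It would say nothing about CBD against vehicle.
2. **Complete rows.** The classical ANOVA needs every scheduled value from a person. One missed day out of five consecutive days removes that person from the serial analysis. With 15 per arm this matters for the per-visit estimates meant to plan a larger trial.
3. **One-value outcomes.** A group-by-time ANOVA and Friedman's test both need repeated values, so neither can analyse a peak or a duration.
4. **Sphericity.** Soreness probably varies little at Visits 1 and 2 and much more afterwards. An uncorrected interaction test, which opens the post-hoc comparisons, is then somewhat liberal.

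**Working it through.** The plan states no power, SD, effect size or attendance rate, so it has no figure to reproduce. Inputs from the documents: 15 per arm, six visits, two-way ANOVA, alpha 0.05 (taken as two-sided). All other inputs are assumptions.

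**Friedman's test.** It ranks the visits within each person. A constant added to all of a person's values leaves those ranks unchanged. Adding 5 units to every value in one simulated arm left the statistic at 103.695 before and after. With identical arms and visit means of 0.2, 0.2, 3, 3.5, 2.5 and 1.5 cm, it was significant in 2,000 of 2,000 simulated trials.

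**Complete rows.** Visit 1 is always observed, and each later scheduled visit is missed independently at rate m. Expected rows = 30 × (1 − m)^k, where k counts the later visits.

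| Outcomes | k | m = 5% | m = 10% |
|---|---|---|---|
| Soreness, LEFS, PCS | 5 | 23.2 | 17.7 |
| MVIC, TSCT | 5 | 23.2 | 17.7 |
| QST, FPQ-9, PASS-20, PSQI | 2 | 27.1 | 24.3 |

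Permanent dropout of 5% per visit also leaves 23.2 complete rows. But 27.1, 25.7, 24.4 and 23.2 people are still seen at Visits 3 to 6.

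**Interval width for soreness at one visit** (SD 2 cm). Half-width = t × SD × √(1/n1 + 1/n2).
- 15 + 15: 2.048 × 2 × 0.365 = 1.50 cm.
- 12 + 11 complete rows: 2.080 × 2 × 0.417 = 1.74 cm.
- Mixed model on all available visits (simulated): 1.51 cm with 5% isolated gaps, 1.60 to 1.62 cm with 5% dropout.

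**Power, like for like.** Assume SD 0.3 cm at Visits 1 and 2 and 2 cm at Visits 3 to 6. Correlation is 0.5 within each period and 0.1 between them. The effect is 0.6 SD, or 1.2 cm, at Visits 3 to 6 only. The fair comparator is the ANOVA's group main effect, because it also tests an average arm difference.
- Main effect: mean over six visits. Difference = 4 × 1.2/6 = 0.80. Variance of the six-visit sum = 40 (Visits 3 to 6) + 0.27 (Visits 1 and 2) + 0.96 (cross terms) = 41.23. SD of the mean = √41.23/6 = 1.070. Standardised effect = 0.748.
- Mean over Visits 3 to 6: SD = √(40/16) = 1.581. Standardised effect = 1.2/1.581 = 0.759.
- With 15 + 15, noncentrality = effect × √7.5 = 2.05 and 2.08, so power is about 51% and 52%.
- With 12 + 11 complete rows, the main effect has noncentrality 0.748 × √(132/23) = 1.79, so power is about 40%.

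Simulation of both analyses agrees:

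| Missing data | Complete-row main effect | All available visits, mean over Visits 3 to 6 |
|---|---|---|
| None | about 52% | about 53% |
| 5% isolated gaps | about 39% | about 52% |
| 5% dropout per visit | about 39% | about 45% |

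**Sphericity.** With the same SDs, no arm effect and complete data, four correlation patterns were run with 6,000 simulated trials each. The uncorrected interaction test rejected in 6.0% to 10.2%. With Greenhouse-Geisser it rejected in 3.6% to 5.2%.

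**Visit 1 covariate.** Interval width is multiplied by √(1 − r²) against no adjustment: 0.866 at r = 0.5, and 0.995 at r = 0.1, which is more like soreness.

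**Replacement rank test.** A rank-sum test of arm on each person's mean over Visits 3 to 6 had type I error of 4.4% to 5.0%. At correlation 0.5 its power was 48% with no gaps and 47% with 5% gaps.

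**The case against.** Friedman's test is only an example. A reader might infer that skewed data must lead to it, but the wording allows another test. What stands is that no test comparing the arms is named.

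A reader might also infer that the mixed model gains soreness power even with complete data. That comes from setting the ANOVA's interaction test (39% with Greenhouse-Geisser, at correlation 0.5) against a mean arm difference (53%). These are different hypotheses. The plan ties post-hoc tests to the interaction, but nothing in it excludes the group main effect, and against that test the gain with complete data disappears.

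Missing data are assumed. The study lasts 15 days and rewards attendance, so losses may be few. The stopping criteria count as lost to follow-up anyone "failing to attend planned study visits or failure to respond to contacts by study personnel after documented 2 attempts", so permanent dropout may be commoner than isolated gaps, and there the gain is smaller. Nor does every interval widen: a peak or a duration need not be lost because one visit is.

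Small-sample mixed models carry their own risk. A Satterthwaite joint test on an unstructured model had type I error of 8% to 11% in simulation, no better than the uncorrected ANOVA. Kenward-Roger held 4.2% to 5.7%. This objection stands as a condition on the fix.

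Silence on sphericity does not mean that no correction will be applied, but stating one costs nothing.

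**Conclusion.** The point holds as a cheap improvement. Two parts need no assumption about attendance: the only named distribution-free test cannot make the trial's comparison, and neither named test fits the one-value primary outcomes. The complete-row loss follows from the ANOVA and the absence of any missing-visit rule. Its size depends on attendance, which the documents do not give: no gain with complete data, about 13 points of power with 5% isolated gaps (39% to 52%) and about 6 points with 5% dropout per visit (39% to 45%). These figures assume a 0.6 SD effect at Visits 3 to 6 and correlation 0.5. The 6% to 10% type I error assumes SDs of 0.3 cm before exercise and 2 cm after.

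A reader might go further and conclude that 15 per arm is too few or that the trial will fail. The documents do not support that: the study is described as exploratory and sets no power target.

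**What to change.** 1. Replace Friedman's test with a rank-sum or permutation test of arm on a per-person summary.
2. Analyse peak soreness, soreness duration and peak disability as two-group comparisons.
3. For serial outcomes, fit a mixed model by REML to all available visits of all randomised participants in their assigned arm. Report the arm difference with its 95% interval at each visit. For soreness, model Visits 3 to 6 and name the mean arm difference over them as the leading contrast. Use Kenward-Roger degrees of freedom. Check first that the named software offers them; if not, use a permutation p-value for arm.
4. Apply Greenhouse-Geisser wherever a repeated-measures ANOVA is kept.
5. Adjust the questionnaires and QST for their Visit 1 value. This adds almost nothing for soreness and perhaps little for LEFS, which should start near its ceiling. MVIC and TSCT are first taken at Visit 2, on product, so they have no such covariate.
6. Report missed visits and dropout by arm and reason.

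**Cost.** Analysis wording, slightly more analysis work and one degree of freedom per covariate; no change to visits or data. A mean over Visits 3 to 6 has little power for an effect confined to one visit: 8% for Visit 4 alone at correlation 0.5, against 26% for the corrected interaction test. The model does not recover soreness data from people who leave before any post-exercise visit, and does not cure dropout that depends on unseen values.

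### Most outcomes have a value taken before randomisation, but the planned ANOVA does not use it as a covariate, so arm differences, mainly for the questionnaires and QST, are less precise than the data allow

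*Combined protocol and SAP*

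**What the plan says.** The analysis is set out in section 6, Data Management & Analysis: "Outcome measures will be analyzed using a two-way ANOVA with repeated measures (between-group; within-time"), or a distribution-free test if the data call for one. "Statistical significance will be set at p<0.05". The follow-up step is: "If significant interactions occur, the Tukey post-hoc test will be used to reveal where the differences occur". Effect sizes and measures of precision are promised for all outcomes. No covariate is named, and the visits that make up the time factor are not listed.

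The Visit 1 section gives the order of events on Day 1: "The participant will complete several psychological questionnaires (FPQ-9, PCS, PASS-20, PSQI, & LEFS), followed by tests for muscle soreness and quantitative sensory testing (QST"). After that, "Participants will then be randomly assigned to an experimental group". These measures therefore precede both allocation and the first dose.

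The later schedule differs by outcome:
- PCS, LEFS and soreness are repeated on Days 11 to 15, which makes six visits with Day 1.
- FPQ-9, PASS-20, PSQI and QST are repeated on Days 11 and 15, which makes three visits.
- Leg function, namely "the timed stair climbing test (TSCT) and isometric strength measures to evaluate leg function", is first scheduled at Visit 2 (Day 11), after ten days of dosing.

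Study Location & Design gives the size: "Participants will be randomly assigned to either an active CBD dose group (n=15) or vehicle-control (placebo) group (n=15"). It refers to both a pre-supplement and a pre-exercise baseline and does not say which one the analysis uses.

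**The concern.** At Day 1 the arms can differ only by chance. The Day 1 value therefore carries no information about treatment, but it does carry information about how each person will score later. A covariate term uses that information to reduce the error of the arm comparison. The planned model has no such term.

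There are two ways to read the time factor:
- **Day 1 is a time level.** The group main effect is then averaged over a visit at which the true difference is zero.
- **Time starts at Day 11.** The main effect is then the unadjusted mean on-treatment difference, and the pre-randomisation value is not used at all.

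Neither reading gives a baseline-adjusted arm difference. The study's stated purpose is preliminary data for a larger trial, so what is at stake is chiefly the precision of its estimates.

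**Working it through.** **Inputs.** From the documents: 15 per arm, significance level 0.05 (taken as two-sided), and the visit schedule above. The plan states no power, effect size, SD or correlation, so it has no figure to reproduce. Assumed here: equal SDs, equal correlation ρ between any two visits (0.3, 0.5, 0.7), and no dropout.

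**Step 1: dilution of the group main effect if Day 1 is a level.** With a constant effect δ at every visit after Day 1 and T visits in all, the main effect estimates δ(T−1)/T. That is 5/6 of δ for six visits and 2/3 of δ for three.

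**Step 2: gain in precision from the covariate.** Let m be the number of later visits averaged.
- Variance of the mean of m visits: (1 + (m−1)ρ)/m, in units of the single-visit variance.
- Share explained by Day 1: R² = mρ²/(1 + (m−1)ρ).
- CI width ratio, adjusted to unadjusted: about √(1−R²) × 1.021. The factor 1.021 is the small-sample price: √(1 + 1/26) = 1.019 for chance imbalance in the covariate, times the t quantiles on 27 and 28 df, 2.052/2.048 = 1.002.

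| ρ | m = 2 (three-visit outcomes) | m = 5 (six-visit outcomes) |
|---|---|---|
| 0.3 | R² 0.138, ratio 0.948, 5% narrower | R² 0.205, ratio 0.911, 9% narrower |
| 0.5 | R² 0.333, ratio 0.834, 17% narrower | R² 0.417, ratio 0.780, 22% narrower |
| 0.7 | R² 0.576, ratio 0.664, 34% narrower | R² 0.645, ratio 0.608, 39% narrower |

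Simulation at 15 per arm gave 5-9%, 16-22% and 33-38%, within about one point of the formula. Type I error of the adjusted test was 4-6%.

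For the averages recommended under the fix, the same formula gives:
- Days 12-15 (m = 4): R² 0.189, 0.400 and 0.632, so about 8%, 21% and 38% narrower.
- Day 15 alone (m = 1): R² 0.09, 0.25 and 0.49, so about 3%, 12% and 27% narrower.

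**Step 3: power depends on the shape of the effect.** Simulated at 15 per arm with an effect of 0.75 SD:

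| Pattern | ρ | Planned interaction (Day 1 as a level) | Group main effect (Day 1 as a level) | Day 1-adjusted mean of all later visits |
|---|---|---|---|---|
| Six visits, constant from Day 11 | 0.5 | 49% | 56% | 91% |
| Three visits, constant from Day 11 | 0.5 | 53% | 37% | 78% |
| Six visits, Days 12-13 only | 0.5 | 72% | not needed here | 25% |

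The ranking of the interaction and the averaged contrast reverses between the first and last rows.

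**Step 4: soreness-type outcome.** Study Population excludes people with current hip, leg or knee pain, so Day 1 soreness should lie near its floor and LEFS near its ceiling. Assume Day 1 and Day 11 SDs of 0.1 to 0.3 of the post-exercise SD, ρ with Day 1 of 0 to 0.3, correlation 0.7 among post-exercise visits, and a 1.0 SD effect on Days 12-15. Power is then 81-89% for the interaction (Greenhouse-Geisser corrected) and 84-88% for the Day 1-adjusted post-exercise mean. Case by case, the interaction lies between 2.5 points below and 0.6 above.

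**The case against.** Group-by-time ANOVA is a valid analysis, the study is exploratory with no power target, and the plan already promises effect sizes and precision. On that view, adding a covariate is a preference about efficiency. That is fair: no figure in the plan is wrong, and the point concerns efficiency and clarity.

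Three stronger readings are tempting, and the documents do not support them.
- **That neither planned test removes between-person variance.** This is untrue of the interaction, a within-person test whose error excludes each person's own mean. Its power rises with ρ for that reason (49% to 73% as ρ goes from 0.5 to 0.7, six visits, constant effect). Part of its shortfall under a constant effect comes from spreading one effect over 5 or 2 degrees of freedom.
- **That one averaged, adjusted contrast should replace the interaction.** That helps only if the effect is roughly constant. Aim 1 concerns patterns of recovery over time, and the risk section expects symptoms to be much reduced within 4-5 days, so an effect that rises and fades is at least as plausible.
- **That the trial as a whole loses much of its power.** The large gains concern secondary outcomes. For soreness the difference is small (Step 4), and LEFS is probably similar. MVIC and TSCT have no pre-randomisation value to use.

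It is also an inference, though the natural one, that Day 1 is a time level. What survives all of this is that no reading of the plan uses Day 1 as a covariate.

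**Conclusion.** The point holds as a limited one. For every outcome measured on Day 1, the plan leaves a pre-randomisation value out of the arm comparison as a covariate and does not name its analysis baseline or time levels. For the questionnaires and QST this widens the 95% CI of the mean on-treatment difference, compared with an adjusted analysis, to an extent that depends on ρ: negligible to modest at 0.3, material at 0.5, large at 0.7. Those figures rest on equal SDs, equal correlations and complete data, none of which the documents supply.

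The power figures show only that the better test depends on the effect's time course. They do not show a general loss. Peak and duration of soreness give one value per participant, so the quoted model does not fit them directly and the figures here do not describe them.

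**What to change.** In Data Management & Analysis:
1. Name Day 1 as the analysis baseline for every outcome measured then, and list the visits that form the time factor.
2. For those outcomes, take Day 1 out of the response and enter it as a covariate.
3. Keep the group and group-by-visit terms over the later visits. The group term then carries a sustained effect and the interaction carries one confined to a few visits.
4. Report the Day 1-adjusted arm difference, with a 95% CI, at each visit and averaged over the post-exercise visits (Days 12-15, or Day 15 alone where it is the only one). Show the pre-injury Day 11 difference separately. The averaged difference stands beside the group-by-visit test and does not replace it.
5. State that MVIC and TSCT have no pre-randomisation value, so that their Day 11 value is not treated as a clean baseline.

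The cost is a change of wording and one degree of freedom (28 to 27 for the arm comparison). No new data are needed.
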